4.2 Exclusion Criteria

- 1. Aggressive natural killer-cell leukemia or ENKTL patients who have any degree of leukemic involvement will be excluded.
- 2. Concomitant with hemophagocytic lymphohistiocytosis.
- 3. Current or historical primary central nervous system lymphoma (PCNSL) or secondary CNS involvement.
- 4. Prior allogeneic organ transplantation.
- 5. Allogenic hematopoietic stem cell transplantation (HSCT) \leq 5 years before the first dose of investigational product. (Patients are permitted to enroll if they received allogenic HSCT more than 5 years before the first dose of investigational product and without any current graft-versus-host reaction.)
- 6. Current participation in another clinical study or use of any investigational drug within 4 weeks before the first dose of investigational product in this trial.
- 7. Autologous HSCT within 90 days before the first dose of CS1001.
- 8. Subjects with an active autoimmune disease that requires systemic treatment in the past two years. (Hormone replacement therapy is not considered as systemic therapy such as the patient has type I diabetes mellitus, hypothyroidism that can be managed with thyroid hormone replacement only, or adrenal insufficiency or pituitary insufficiency that requires a physiological dose of corticosteroid replacement.) Subjects are permitted to enroll if they have an autoimmune disease that didn't require any systemic treatment in the past two years.
- 9. Subjects received systemic corticosteroid or any other immunosuppressive therapy within 14 days before the first dose of the investigational product. [Subjects are permitted to use topical, ocular, intra-articular, intranasal and inhaled corticosteroids (with minimal systemic absorption); a short course (≤ 7 days) of corticosteroids for prophylaxis (e.g., hypersensitivity to contrast media) or for treatment of non-autoimmune conditions (e.g., delayed hypersensitivity caused by contacting allergens).]
- 10. A known additional malignancy within 5 years prior to the first dose of investigational product. Subjects with locally curable malignancies (including basal

cell carcinoma of skin, squamous cell carcinoma of skin, breast cancer in situ or cervical cancer in situ, etc.) that have undergone curative therapy are permitted to enroll.

- 11. Subjects who have had prior chemotherapy, immunotherapy, biological therapy (including cancer vaccine, cytokine therapy or growth factors to treat cancer) used as a systemic treatment for cancer, within 28 days before the first dose of investigational product.
- 12. Subjects who underwent a major surgical procedure within 28 days prior to the first dose of investigational product or radiotherapy within 90 days before the first dose of investigational product.
- 13. Any use of traditional Chinese medicines or herbal preparations with anti-tumor indications within 7 days before the first dose of investigational product.
- 14. Has received a live vaccine within 28 days before the first dose of investigational product. (Attenuated influenza vaccine is allowed.)
- 15. Known history of (HIV infection and/or acquired immune deficiency syndrome (AIDS).
- 16. Subjects at the active phase of chronic hepatitis B or with active hepatitis C. Subjects who are HBsAg positive or HCV antibody positive at screening must not be enrolled until further definitive testing with HBV DNA titers (≤ 2500 copies/mL or 500 IU/mL) and HCV RNA tests (\leq the lower limit of detection) can conclusively rule out the presence of active hepatitis B or C that requires treatment, respectively. Subjects that carry the hepatitis B virus, with stable hepatitis B (HBV DNA titer ≤ 2500 copies/mL or 500 IU/mL) after medical treatment or with cured hepatitis C are permitted to enroll.
- 17. History of interstitial lung disease (except for those induced by radiation therapies and are asymptomatic).
- 18. Active tuberculosis infection.
- 19. An active infection requiring systemic anti-infection therapy within 14 days before the first dose of investigational product.
- 20. Subjects who have received anti-PD-1, anti-PD-L1, or anti-CTLA-4 monoclonal antibody treatment.
- 21. Subjects with a known severe allergy to monoclonal antibodies (≥ Grade 3 per CTCAE v 4.03) or uncontrolled allergic asthma.
- 22. Women in pregnancy or lactation.
- 23. Subjects with active alcohol or drug dependence..
- 24. Subjects with uncontrollable concomitant diseases including but not limited to symptomatic congestive heart failure, uncontrolled hypertension, unstable angina, active gastrointestinal ulcer or hemorrhagic disorders.
- 25. Subjects with a history of psychiatric disease; or subjects with incapacity or limited capacity.
- 26. Underlying condition that in the investigator's opinion would increase the risk of investigational product administration or confound the assessment for its toxicity.
- 27. Subjects in the investigator's opinion are not suitable for participating in this trial.

4.3 Discontinuation and Withdrawal

4.3.1 Discontinuation of Study Treatment

Subjects must discontinue study treatment if any of the following criteria are met:

- 1. Any AE that meets the treatment discontinuation criteria specified in the protocol (refer to Section 5.3).
- 2. Disease progression. (Subject who meets the criteria for treatment beyond progression may continue treatment until confirmation of progressive disease by tumor assessment. Refer to Section 3.1.2.1.)
- 3. Subjects who receive any prohibited treatment during the trial that compromises the assessment of safety and efficacy may be determined to discontinue study treatment by the investigator in consultation with the sponsor medical monitor.
- 4. Any intercurrent condition that compromises the subject's ability to continue study treatment.
- 5. Pregnancy of female subjects.
- 6. Subjects and/or their legal guardian who decide to discontinue the study treatment may inform the subject's doctor at any time and then discontinue study treatment. According to the Deceleration of Helsinki and other applicable regulatory requirements, all subjects have the right to withdraw from the study at any time and for any reason. The doctor and the study site must not hold bias in their future treatment.
- 7. Subject with poor compliance who doesn't receive treatment at the right dose and the right time despite the investigator's effort in communication and coordination, which may lead to significant uncorrectable bias in the study results may be determined to discontinue study treatment by the investigator in consultation with the sponsor medical monitor.
- 8. Other conditions that make study treatment continuation inappropriate judged by the investigator.

In any case, the primary reason for study treatment discontinuation will be recorded in the original medical record. For subjects who discontinue study treatment for any reason, the investigator should try every effort to have the subject complete end of study visit if the subject has received at least one dose of the investigational product, and continue to follow up subjects with unresolved AE.

4.3.2 Follow-up After Discontinuation

Subjects who discontinue study treatment must be followed up. Outcome and/or survival follow-up data will be collected per protocol requirements until the subject dies or this study ends. Apart from subjects who discontinue treatment due to radiological disease progression assessed by imaging, tumor assessment should be performed at pre-specified regular time points until radiological disease progression, the start of new anti-cancer treatment, death, or the end of this trial, whichever occurs first.

Study sites will contact subjects who are lost to follow-up, if possible, determine the reason for lost to follow-up, and rearrange follow-up visits. The date of contacting the subject and contact method will be recorded in the study file.

4.3.3 Consent Withdrawal

If a subject that requires study treatment discontinuation would continue the study, he/she must follow the follow-up procedures specified in the study protocol. The only exception

allowed is that the subject clearly withdraws the informed consent and himself/herself or other authorized personnel who provides this information cannot be contacted. The subject shall inform the investigator by a written notice about the decision to withdraw the consent to future follow-up, if possible. The investigator should record the details in the subject's medical record, including whether the consent withdrawal refers to study treatment discontinuation only or no more study procedures and/or post-discontinuation follow-up. Only data that allowed to be disclosed in compliance with legal and applicable regulatory requirements can be used for survival evaluation.

4.4 Definition of WOCBP

Women of childbearing potential (WOCBP) refer to women that have had menarche, haven't received any sterilization operation (such as hysterectomy or bilateral oophorectomy), and haven't reached menopause. Menopause is defined as amenorrhea for over 12 months without any biological or physiological cause in women aged >45 years. Furthermore, the documented follicular stimulating hormone (FSH) level of women aged <55 years must be > 40 mIU/mL to confirm menopause.

* The FSH level of women on hormone replacement therapy (HRT) may be artificially suppressed. These women may need a washout period to obtain a physiological FSH level. The duration of the washout period is determined by the type of HRT. Guidelines recommend the following duration of the washout period. Investigators should determine the washout period at their own discretion when testing for serum FSH levels. Women whose serum FSH level is > 40 mIU/mL at any time during the washout period can be considered as menopause.

- At least one week for vaginal contraception products (such as vaginal ring, contraceptive jelly, and gel)
- At least 4 weeks for transdermal products
- At least 8 weeks for oral contraceptive agents

May need at least 6 months for other parenteral products.

4.5 Definition of Effective Contraception

Subjects must be willing to use at least two methods of contraception; one is a highly effective method and the other highly or less effective method as listed below. If total abstinence is used as a highly effective method, other methods will not be needed.

Highly effective contraception methods

WOCBP subjects or WOCBP partners of male subjects may use hormonal methods of contraception, for example, compound oral contraceptives, vaginal ring, injections, implant, or intrauterine device. The female partners of male subjects enrolled in this study may use hormonal contraceptive pills as an acceptable method of contraception because they don't receive investigational product administration.

Intrauterine device Tubal ligation Vasectomy Total abstinence* * Total abstinence defined as total avoidance of heterosexual intercourse is an acceptable method of contraception for all investigational products. Female subjects must continue to receive a pregnancy test. When a subject is no longer in total abstinence, other acceptable highly effective methods of contraception must be considered.

Less effective contraception methods

Male condom that contains spermicide

Contraceptive diaphragm that contains spermicide

Cervical cap that contains spermicide

Vaginal sponge

Male condom that doesn't contain spermicide

WOCBP subject or WOCBP partner of a male subject takes pills that only contain progesterone

Female condom*

* Male condom and female condom should not be used at the same time.

5. STUDY TREATMENT

5.1 INVESTIGATIONAL PRODUCT

The investigational product in this protocol is CS1001,

The investigational treatment regimen is CS1001, 1200 mg, IV infusion Q3W.

5.1.1 Dosage Form and Specifications

Dosage form: injection

Specifications: 90 mg/3 mL/vial and 600 mg/20 mL/vial

Excipients: histidine/histidine hydrochloride, mannitol, sodium chloride, Polysorbate 80; pH 5.5

Period of validity: 36 months, tentatively.

Storage condition: 2 °C to 8 °C

5.1.2 Packaging and Labeling

CS1001 is for injection with specifications of 90 mg/3 mL/vial and 600 mg/20 mL/vial. All investigational products will be labeled in compliance with Good Clinical Practice (GCP) requirements. The label content will be designed according to the sponsor's standards. All drugs will be dispatched as the main trial-specific materials.

A uniform format will be applied to the drug labels. The labeling will contain the following information: protocol number, name of the investigational product (and "For clinical trial use" labeled), specification, storage, batch number, expiry date, and sponsor.

All the records of batch number and expiry date as well as labels for all investigational products will be kept in the study file.

5.1.3 Management of Investigational Product

The investigational product handling liability will be executed as per requirements in Appendix 13.3.

5.1.3.1 Dispensing of Investigational Products

The investigational product is provided by the sponsor, dispatched to the study sites as per the plan. The investigational product must be kept and dispensed by a designated person at the study site. The investigational product will be stored in a locked cabinet as required.

5.1.3.2 Storage of Investigational Product

The investigational product will be kept, handled, and dispensed by a designated person at the study site. The responsible person at the study site will confirm the receipt of investigational product in writing and use the investigational product within the framework specified in the protocol. An accurate record of the shipment, dispensing, and return of the investigational product will be maintained. Meanwhile, the sponsor will retrieve the packages of investigational product at the end of this trial. The storage temperature of investigational products will also be recorded in corresponding documents.

The investigational product will be dispensed by a member of the study team. The personnel should ensure and record the dispensing of the investigational product as planned; the quantity of dispensed and returned drugs and corresponding dates will be recorded in the source medical record.

5.1.3.3 Return of Investigational Product

The investigational product will be returned in the study. All unused and/or partially used investigational product(s) will be returned to and destroyed by a third party designated by the sponsor following the accountability work at the study site.

5.1.3.4 Destruction of Investigational Product

The investigational product will be destroyed at a third party designated by the sponsor. Study personnel should ensure, develop, and record an adequate process of investigational product handling in compliance with applicable regulations, guidelines, and policies. The investigational product will be destroyed per sponsor's approval.

5.1.4 Preparation and Administration

CS1001 is to be administered as an IV infusion in compliance with local clinical guidelines. (Infusion using a device through a 0.2 micrometer in-line or with an additional filter is recommended.) See the *Drug Handbook* for additional information on preparation and other special requirements.

Dilution:

• Dilute the total dose of CS1001 to be administered with 250 mL of sterile normal saline (0.9% sodium chloride solution).

Administration Instructions

- CS1001 is to be administered as an IV infusion, not an IV bolus injection.
- Ensure that the investigational product is clear, colorless, and free from any particulate matter on visual inspection.
- Withdraw a total of 40 mL (13.33 vials of 90 mg/3 mL/vial product, or 2 vials of 600 mg/20 mL/vial product) of CS1001 solution into a syringe. The solution of the two specifications should not be mixed for a single infusion. Inject CS1001 solution withdrawn into a 250-mL infusion bag of normal saline. Do not insert a syringe into a vial to withdraw investigational products more than once. Do not use a glass syringe to withdraw investigational products.
- Mix by **gently** inverting several times. Do not shake.
- Visually inspect the final solution. If the solution is not clear or the contents appear to contain precipitate, the solution should be discarded and record in the drug management log.
- Record time and dose (in mg) of CS1001 preparation in the preparation sheet.
- The investigational product is administered over 60 minutes. For subjects who have an infusion-related reaction, the infusion duration can be extended appropriately, according to Section 5.3.4. The infusion line should not be used for other medication infusions.
- The infusion line should undergo flush with sufficient normal saline at the end of the infusion.
- The investigational product is recommended to be administered to subject immediately after preparation, avoiding exposing the prepared solution under room temperature for more than the recommended *6-hour limit*. In which, the 6 hours include the time for CS1001 storage under room temperature, solution storage in the infusion bag, and infusion time. If the administration of the prepared drug is to be postponed, it should be stored under refrigeration at 2 °C to 8 °C for no more than **24 hours**.

5.2 TREATMENT COMPLIANCE

The dosing of the investigational product will be monitored by the principal investigator or his/her assistant for ensuring treatment compliance. The exact time of dosing (starting and ending of infusion) and dose administered should be recorded. For infusion interruption, the cause of interruption should be recorded in eCRF.

5.3 INVESTIGATIONAL PRODUCT DOSING MODIFICATION

5.3.1 Overall Principle for Investigational Product Dosing Modification

The mechanism of CS1001 is to promote T-cell activation and proliferation. As a result, CS1001 may induce autoimmune hyperactivity which will further cause autoimmune diseases involving multiple organ systems. Immune-related AEs (irAEs), for example, pneumonitis, diarrhea/enterocolitis, renal impairment, rash, hepatitis, endocrine disorders, and peripheral or central neuropathy have occurred in the clinical use of other immune checkpoint inhibitors including ipilimumab, nivolumab, pembrolizumab, and atezolizumab. Once a subject develops any of the above AEs in this trial, the subject should be monitored for symptoms and signs. Appropriate tests and examinations may be conducted for differentiating etiology. If no other cause (for example disease progression, concomitant medication, or infection) is found while the subject requires corticosteroid and/or other immunosuppressive treatment, the AE is considered as related to the immune system hyperactivity caused by CS1001, and thus is an irAE. (This rule doesn't apply to endocrinology events, for example, hyperthyroidism/hypothyroidism, hypophysitis, type I diabetes mellitus, and adrenal insufficiency, which will still be considered as related to autoimmune hyperactivity caused by CS1001 treatment although they may not require immunosuppressive treatment). Identification, diagnosis, management, and dose modification for irAEs are detailed in Appendix 13.4.

5.3.2 Criteria for Dose Modification of Investigational Product

Dose increase or reduction of CS1001 is not permitted in this trial. The investigational product will be **withheld** for any of the following investigational drug-related adverse reactions:

- 1. Grade 2 pneumonitis
- 2. Grade 2 or 3 colitis; Grade 3 diarrhea or persistent Grade 2 diarrhea
- 3. Grade 2 hepatitis (elevation of ALT, AST, or total bilirubin levels)
- 4. Grade 2 hypophysitis without adrenal crisis
- 5. Grade 2 nephritis
- 6. Grade 3-4 hypothyroidism
- 7. Grade 3 hyperthyroidism lasting for 6 weeks or more despite proper management
- 8. Grade 3 dermatitis
- 9. Grade 2 neuromuscular toxicity
- 10. Grade 2 ocular toxicity
- 11. Other Grade 2 AEs (for example arthritis, pancreatitis, hemolytic anemia, adrenal insufficiency, myasthenic syndrome, and rhabdomyolysis)
- 12. Grade 4 hematologic toxicity
- 13. Any Grade 3 abnormal laboratory test results except for the following situations:
 - Grade 3 hematologic toxicity.

- Study treatment will be delayed when Grade 2 hepatitis occurs.
- 14. Any AE, abnormal laboratory test result, or intercurrent condition that in the investigator's opinion requires postponing study treatment.

Subjects may resume investigational treatment when the above AE(s) resolve(s) to Grade 0/1 or baseline and the dose of systemic corticosteroid for treating the AE(s) have been tapered to 10 mg daily prednisone equivalents or less.

The investigational treatment will not be resumed for dosing delay due to any cause for more than **9 weeks** (12 weeks after the last dose). (Subject may continue treatment if he/she still benefits clinically at the discretion of investigator in consultation with the sponsor's medical monitor.)

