- g) Coagulation functions: INR $\leq 1.5 \times$ ULN; PT and APTT $\leq 1.5 \times$ ULN (unless the subject is on anti-coagulant; and PT and APTT at screening are as expected in patients on anti-coagulant).
- 10. Subjects with prior anti-cancer treatment can only be enrolled when the toxicity of prior anti-cancer treatment has recovered to baseline or \leq Grade 1 according to CTCAE v4.03. For patients with irreversible Grade 2 toxicities (e.g. thrombocytopenia, anemia, neurotoxicity, alopecia, and hearing impairment) that is anticipated to be unlikely to worsen during study treatment, the subject can be enrolled after approval by the medical monitor of the sponsor.
- 11. WOCBP must have a negative serum pregnancy test ≤7 days before the first dose of investigational product. WOCBP or fertile men and their WOCBP partners must agree to use an effective contraceptive method from providing signed ICF through 6 months after the last dose of the investigational product (Refer to Section 4.1.5 for details).

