5.3.3 Criteria for Permanent Discontinuation of Investigational Treatment

The investigational product will be **permanently discontinued** after consultation with the sponsor's medical monitor for any of the following drug-related adverse events:

- Grade 3-4 pneumonitis
- Grade 4 colitis, recurrent Grade 3 colitis, or colitis with symptom suggestive of intestinal perforation
- Grade 3 hepatitis (elevation of ALT, AST, or total bilirubin levels)
- Grade 4 abnormal laboratory test results except for the following situations:

-Grade 4 neutropenia lasting for \leq 5 days

-Grade 4 lymphocytopenia or leukopenia

- Solitary Grade 4 electrolyte disorder/imbalance that can be corrected by electrolyte supplementation/adequate treatment in 72 hours without any clinical consequence.

- Grade 3-4 hypophysitis or adrenal crisis
- Grade 3-4 nephritis
- Grade 4 hyperthyroidism
- Grade 4 dermatitis
- Grade 3-4 neuromuscular toxicity
- Grade 3-4 ocular toxicity
- Other Grade 3-4 AEs (for example arthritis, pancreatitis, hemolytic anemia, adrenal insufficiency, myasthenic syndrome, and rhabdomyolysis) except for Grade 3/4 hypothyroidism
- Grade 4 infusion-related reactions

Permanent discontinuation of investigational product will be considered for recurrence of any of the following Grade ≥ 2 irAEs: pneumonitis, ocular toxicity, cardiac toxicity, and at the discretion of the investigator.

For subjects who meet any of the above criteria although benefiting from investigational treatment, the sponsor's medical monitor and the investigator will discuss and make the final decision in the subject's best interest.

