7.3.2 Assessment of Severity

For any AE, whether it is fatal or life-threatening, whether it leads to persistent or permanent disability, requires or prolongs hospitalization, or causes congenital anomaly will be recorded and graded based upon CTCAE v4.03. For an AE that is related to abnormal laboratory test finding(s), the event will be graded according to the clinical severity of the underlying condition; the grade is not necessarily in line with the grade of laboratory test finding.

Intensity will be graded based upon the following rules:

Grade	Description
-------	-------------

Grade 1	Mild; asymptomatic or mild symptoms; clinical or diagnostic observations only; or intervention not indicated	
Grade 2	Moderate; minimal, local, or non-invasive intervention indicated; or limiting age appropriate instrumental activities of daily living*	
Grade 3	Severe or medically significant, but not immediately life threatening; hospitalization or prolongation of hospitalization indicated; disabling; or limiting self care activities of daily living**	
Grade 4	Life-threatening consequences or urgent intervention indicated	
Grade 5	Death related to adverse event	

* Instrumental activities of daily living refer to preparing meals, shopping for groceries or clothes, using the telephone, financial management, etc.

** Examples of self-care activities of daily living include bathing, dressing, and undressing, taking food, using the toilet, and taking medications, as performed by patients who are not bedridden.

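### The restart permission in Protocol 5.3.2 reaches Grade 4 hematologic events that 5.3.3 by default stops permanently; separately, the restart grade after Grade 3 dermatitis differs between 5.3.2 and Appendix 13.4

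*Protocol*

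**What the plan says.** Protocol 5.3.2 lists drug-related reactions for which dosing is withheld. Item 12 is "Grade 4 hematologic toxicity", without qualification. One restart sentence covers the whole list: "Subjects may resume investigational treatment when the above AE(s) resolve(s) to Grade 0/1 or baseline", provided any corticosteroid has been tapered to 10 mg prednisone equivalent a day or less. Delays over 9 weeks end treatment unless the investigator and the medical monitor agree otherwise.

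Protocol 5.3.3 lists drug-related events for which treatment ends permanently after consultation with the medical monitor. One entry is "Grade 4 abnormal laboratory test results except for the following situations". The exceptions are neutropenia of 5 days or less, lymphocytopenia or leukopenia, and an isolated electrolyte disorder corrected within 72 hours. A separate entry names Grade 3-4 hemolytic anemia. The last paragraph leaves the final decision to the monitor and investigator jointly when a subject who meets a criterion is benefiting.

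Protocol 4.3.1 makes the stop rules mandatory: "Subjects must discontinue study treatment if any of the following criteria are met". Its first criterion covers adverse events that meet the discontinuation criteria of Section 5.3.

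For Grade 3 dermatitis, 5.3.2 (item 8 with the restart sentence) requires recovery to Grade 0/1 or baseline. Appendix 13.4 withholds only until Grade 2 or lower. Section 5.3.1 sends readers to Appendix 13.4 for dose modification of immune-related events.

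**The concern.** A site handling a Grade 4 cytopenia will naturally look in 5.3.2, find the event in item 12, and read on to a restart rule that has no exception. An ordinary restart there requires no call to the medical monitor; the monitor appears only for delays over 9 weeks. The safeguards in 5.3.3 work only if the site sees that 5.3.3 applies.

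The stake is patient safety: re-dosing after a Grade 4 event for which the next section's default is a permanent stop. There is a minor reporting consequence too. The SAP (Adverse Events) summarises treatment-emergent events leading to discontinuation or interruption, so sites that read the sections differently would report the same event differently.

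**Working it through.** No arithmetic applies; the check sets the rules side by side.

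**1. Do both lists cover the same events?** Yes. Both are confined to drug-related events.

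**2. Are cytopenias laboratory results in this protocol?** Yes. Item 13 of 5.3.2, "Any Grade 3 abnormal laboratory test results except for the following situations", gives Grade 3 hematologic toxicity as an exception, which would be needless if cytopenias were not laboratory results. The 5.3.3 exceptions for neutropenia, lymphocytopenia and leukopenia presuppose the same.

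**3. Which Grade 4 hematologic events meet both rules?**

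| Drug-related Grade 4 event | 5.3.2 item 12 and restart sentence | 5.3.3 default | Result |
|---|---|---|---|
| Neutropenia, 5 days or less | withhold, may restart | excepted | consistent |
| Lymphocytopenia or leukopenia | withhold, may restart | excepted | consistent |
| Neutropenia, over 5 days | withhold, may restart | permanent stop | mismatch |
| Thrombocytopenia | withhold, may restart | permanent stop (not excepted) | mismatch |
| Hemolytic anemia | withhold, may restart | permanent stop (named; Appendix 13.4 agrees) | mismatch |

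The neutropenia and thrombocytopenia rows assume Grade 4 as a laboratory result. Section 7.3.2 says of an adverse event tied to a laboratory finding that "the grade is not necessarily in line with the grade of laboratory test finding". Section 5.3.3 does not name thrombocytopenia; the stop follows from the general laboratory entry.

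The hemolytic anemia row shows that the literal reading cannot be intended. Grade 3 is a stop under 5.3.3 and is not in the withhold list by name (item 11 covers Grade 2), yet Grade 4 would fall under item 12 and be allowed to restart.

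**4. A concrete case.** Inclusion criterion 10 says: "For patients with irreversible Grade 2 toxicities (e.g. thrombocytopenia, anemia, neurotoxicity, alopecia, and hearing impairment") unlikely to worsen, entry is possible with the medical monitor's approval. Such a subject's baseline is Grade 2 thrombocytopenia. After a drug-related Grade 4 fall, the 5.3.2 sentence would permit restart on return to Grade 2. The 5.3.3 default is to stop, unless the joint decision for benefiting subjects goes the other way.

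**5. Dermatitis.** At Grade 3 both places withhold. A subject who has improved to Grade 2 is dosed under Appendix 13.4 and still withheld under 5.3.2 (unless Grade 2 is baseline). Appendix 13.4 is coherent in itself, because it also continues dosing when dermatitis is Grade 2 or lower.

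**6. How it may have arisen (inference).** The Version 3.0 amendment table lists 5.3.2 items 13 and 14 and the Grade 4 laboratory entry in 5.3.3 as additions. Item 12 is not among them, so it was probably not reconciled with the new entry.

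**The case against.** The best reply is that the sections form tiers: 5.3.2 gives broad triggers to withhold and 5.3.3 escalates some of them. Colitis has this form: Grade 3 is withheld, recurrent Grade 3 is stopped. A mandatory stop in 4.3.1 and a permission in 5.3.2 can also be obeyed together, by stopping. Item 12 is needed in its broad form, because nobody knows on the first day whether neutropenia will last more than 5 days, and the 5.3.3 stop follows a consultation during which dosing must already be on hold.

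Most of this stands. It settles the probable intent, and it rules out narrowing item 12 itself, which would make the immediate withhold unclear. It does not repair the restart sentence, which covers all listed events without a word about 5.3.3. No text expressly ranks the two sections.

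On dermatitis, the reply is that 5.3.1 already points to Appendix 13.4 and that 5.3.2 is the more cautious rule. That makes it an editorial mismatch with no demonstrated harm, but 5.3.2 states its own rule and does not defer.

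**Conclusion.** The point holds as an unqualified restart permission, correctable by one clause. Three drug-related Grade 4 events are affected (thrombocytopenia, neutropenia over 5 days, hemolytic anemia), plus one restart-grade mismatch for dermatitis. It is worth correcting because the text as written permits re-dosing after events that by default end treatment.

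A reader might infer more than the documents support:

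- *That the protocol instructs sites to re-dose, or contradicts itself beyond repair.* It does not: 5.3.2 only permits, 4.3.1 requires, and the sections can be read together.
- *That 5.3.3 is an absolute stop.* It is a default, reached after consultation and open to a joint decision for benefiting subjects.
- *That laboratory Grade 4 anemia is a further case.* The documents do not reproduce the CTCAE thresholds, so this cannot be checked and it is not counted.
- *That the number of affected subjects can be estimated.* No incidence is given, and a percentage for one subject would only restate the number treated.
- *That the primary result is at risk.* There is no effect on the ORR analysis or sample size.

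The conclusion assumes that cytopenias count as laboratory results (step 2) and that hemolytic anemia counts as hematologic toxicity under item 12.

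**What to change.** Leave item 12 as an immediate withhold for all drug-related Grade 4 hematologic toxicity. Add to the restart sentence in 5.3.2: *unless the event meets a 5.3.3 criterion (for example Grade 4 thrombocytopenia, or Grade 4 neutropenia lasting more than 5 days), in which case 5.3.3 applies and treatment is not resumed without the joint decision described there.* Worded this way, the clause also covers hemolytic anemia and recurrent Grade 3 colitis.

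For dermatitis, add to the same sentence: *except Grade 3 dermatitis, which follows Appendix 13.4.* This fits the reference in 5.3.1 and the Grade 2 row of the appendix. If the sponsor prefers the more cautious rule, change the appendix restart grade to Grade 1 instead.

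The cost is one clause for each point, by clarification letter or amendment. No extra subjects, visits or analyses are needed.
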